APPENDIX D. LUGANO CLASSIFICATION FOR RESPONSE ASSESSMENT (CT-BASED ONLY)

Site	CT-Based Response
	Complete radiologic response (all of the following)
Lymph nodes and extralymphatic sites	Target nodes/nodal masses must regress to ≤ 1.5 cm in LDi.
Nonmeasured lesion	Absent.
Organ enlargement	Regress to normal.
New lesions	None.
Bone marrow	Normal by morphology; if indeterminate, immunohistochemistry negative.
	Partial remission (all of the following)
Lymph nodes and extralymphatic sites	
 • $\geq 50\%$ decrease in SPD of up to 6 target measurable nodes and extranodal sites. • When a lesion is too small to measure on CT, assign 5 mm \times 5 mm as the default. • When no longer visible, 0 \times 0 mm. For a node > 5 mm \times 5 mm but smaller than normal, use actual measurement.
Nonmeasured lesions	Absent/regressed, but no increase.
Organ enlargement	Spleen must have regressed by $> 50\%$ in length beyond normal.
New lesions	None.
Bone marrow	Not applicable.
	Stable disease
Target nodes/nodal masses, extranodal lesions	$< 50\%$ decrease from baseline in SPD of up to 6 dominant, measurable nodes and extranodal sites; no criteria for PD are met.
Nonmeasured lesions	No increase consistent with progression.
Organ enlargement	No increase consistent with progression.
New lesions	None.
Bone marrow	Not applicable.

Site	CT-Based Response
	Progressive disease (requires at least 1 of the following)
Individual target nodes/nodal lesions	
PPD progression:
 
 • An individual node/lesion must be abnormal with all of the following: 
 – LDi > 1.5 cm. – Increase by $\geq 50\%$ from PPD nadir. – Increase in LDi or SDi from nadir: 
 ○ 0.5 cm for lesions ≤ 2 cm. ○ 1.0 cm for lesions > 2 cm. • In the setting of splenomegaly, the splenic length must increase by > 50% of the extent of its prior increase beyond baseline (eg, a 15 cm spleen must increase to > 16 cm). If no prior splenomegaly, must increase by at least 2 cm from baseline. • New or recurrent splenomegaly. • New or clear progression of pre-existing nonmeasured lesions. • Regrowth of any previously resolved lesions. • A new node > 1.5 cm in any axis. • A new extranodal site > 1.0 cm in any axis; if < 1.0 cm in any axis, its presence must be unequivocal and must be attributable to lymphoma. • Assessable disease of any size unequivocally attributable to lymphoma. • New or recurrent involvement of the bone marrow.

CT = computed tomography; EOT = end of treatment; LDi = longest transverse diameter of lesion; MRI = magnetic resonance imaging; PPD = cross-product of the longest transverse diameter and perpendicular diameter; SDi = shortest axis perpendicular to the longest transverse diameter; SPD = sum of the product of the perpendicular diameters for multiple lesions.

APPENDIX E. FOLLICULAR LYMPHOMA INTERNATIONAL PROGNOSTIC INDEX

Follicular Lymphoma International Prognostic Index (FLIPI)

Scoring System		
Parameter	Value	Point Score
Age	>60 years of age	1
Ann Arbor stage	Stage III or IV	1
Hemoglobin level	<120 g/L (12.0 g/dL or 6.37 mmol/L)	1
Serum LDH	>ULN	1
Number of Nodal Sites	>5	1
Risk Group by FLIPI Total Point Score		
Risk Group	Total Point Score	
Low	≤1	
Intermediate	2	
High	≥3	

Abbreviations: LDH , lactate dehydrogenase; ULN, upper limit of normal

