Although FL is a biologically heterogeneous disease with widely varying outcomes, the prognosis for individual patients can be made based on clinical and laboratory findings. The most widely used risk model for FL is the FLIPI, which includes 5 adverse prognostic factors: age older than 60 years, Ann Harbor Stage III to IV, hemoglobin less than 120 g/L, 4 or more involved nodal areas, and elevated serum lactate dehydrogenase (Solal-Céligny et al 2004; Appendix E). [REDACTED]

While effective treatments exist for FL, relapse is frequent and is followed by aggressive disease often leading to death within 1 to 2 years. Based on an analysis of 588 patients receiving R-CHOP as initial FL therapy, approximately 20% of patients experienced early PD, defined as PD within 2 years of diagnosis. The 5-year OS was 50% in the early PD group compared with 90% in patients without early PD (Casulo et al 2015). Thus, despite significant progress in the management of patients with FL, an unmet need exists.

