3.1. Subject Inclusion Criteria

A subject who meets all of the following criteria may be included in the study:

1. Aged 18 years or older.
2. Histologically confirmed, relapsed or refractory, follicular B-cell NHL (FL) Grade 1, 2, and 3a.
3. Ineligible for HSCT.
4. Must have been treated with at least 2 prior systemic therapies.
5. Radiographically measurable lymphadenopathy or extranodal lymphoid malignancy (defined as the presence of ≥ 1 lesion that measures > 1.5 cm in the LD and ≥ 1.0 cm in the LPD) as assessed by CT or MRI.
6. Subjects must be willing to undergo an incisional, excisional, or core needle lymph node or tissue biopsy or provide a lymph node or tissue biopsy from the most recent available archival tissue.
7. ECOG performance status 0 to 2 (see [Appendix C](#)).
8. Life expectancy ≥ 12 weeks.
9. Adequate hematologic, hepatic, and renal function (values must not be achieved with growth factors):
 - a. ANC $\geq 1.0 \times 10^9/L$.
 - b. Hemoglobin ≥ 8.0 g/dL.
 - c. Platelet count $\geq 50 \times 10^9/L$.
 - d. Total bilirubin $\leq 1.5 \times ULN$. Subjects with documented history of Gilbert's syndrome and in whom total bilirubin elevations are accompanied by elevated indirect bilirubin are eligible.
 - e. ALT/AST $\leq 2.5 \times ULN$ or $\leq 5 \times ULN$ in the presence of liver metastases.
 - f. Calculated creatinine clearance ≥ 50 mL/min by the Cockcroft-Gault Equation or the estimated glomerular filtration rate ≥ 50 mL/min/1.73 m² using the Modification of Diet in Renal Disease formula.

10. Willingness to avoid pregnancy or fathering children based on the criteria below:
 - a. Woman of nonchildbearing potential (ie, surgically sterile with a hysterectomy and/or bilateral oophorectomy OR ≥ 12 months of amenorrhea and > 45 years of age.)
 - b. Woman of childbearing potential who has a negative serum pregnancy test (see [Table 7](#)) and who agrees to take appropriate precautions to avoid pregnancy (with at least 99% certainty) from screening through safety follow-up. Permitted methods that are at least 99% effective in preventing pregnancy (see [Appendix A](#)) should be communicated to the subject and their understanding confirmed.

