#### 6.1.2. Disease History

Time since diagnosis, initial grade, initial cytogenetics, initial Ann Arbor staging, initial FLIPI risk category, initial presence of B-symptoms, current grade, current cytogenetics, current Ann Arbor staging, current FLIPI risk category, current presence of B-symptoms, bone marrow involvement at baseline (Yes vs No), bulky disease at baseline (longest diameter ≥ 10 cm vs < 10 cm) at baseline by the IRC, and relapsed/refractory status to the most recent prior therapy

will be summarized and listed for all participants in the FAS. Date of tumor marker tests and test results will be listed.

Time since diagnosis will be calculated as follows:

Time since diagnosis (years) = (Day 1 date – date of diagnosis + 1) / 365.25.

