#### 7.3.2. Subgroup Analyses for Objective Response Rate

Subgroups will be formed based on the following participant characteristics and baseline variables for those participants whose data are available:

- Age: < 65 years,  $\ge 65$  years
- Gender: male, female
- Race: white, others
- Geographic region: Europe, North America, rest of world
- Current FL grade: 1, 2, 3a
- Current Ann Arbor Staging: I-II, III-IV
- Current FLIPI risk category: low (0 1), intermediate (2), high  $(\ge 3)$
- Number of prior systemic therapy regimens:  $< 3, \ge 3$
- Bone marrow involvement at baseline: yes, no, unknown
- ECOG performance status:  $\leq 1 \text{ vs } 2$
- Bulky disease at baseline: longest diameter  $\geq 10$  cm vs < 10 cm at baseline by IRC
- Relapsed/refractory status to the most recent prior therapy: relapsed, refractory, unknown

Subgroups may be further divided or combined based on emerging data. The ORR as determined by IRC and its 95% exact binomial CIs will be provided for participants for each subgroup. A forest plot will be created to summarize the variability in ORR as determined by the IRC for participants across subgroups.

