#### 9.3.2. Laboratory Value Summaries

All test results and associated normal ranges from central laboratories will be reported in SI units. Any laboratory test results and associated normal ranges from local laboratories will be converted to SI units.

When there are multiple laboratory nonmissing values for a participant's particular test at a scheduled visit, central laboratory values have higher priority over local laboratory values. If a tie still exists, the laboratory value with the smallest laboratory sequence number will be used in by-visit summaries.

Numeric laboratory values will be summarized descriptively in SI units, and non-numeric test values will be tabulated when necessary. In addition, line graphs will be provided for ALT, AST, hemoglobin, platelet counts, leukocytes, neutrophils, and lymphocytes.

Shift tables will be presented showing change in CTCAE grade from baseline to worst grade postbaseline. Separate summaries for abnormally high and abnormally low laboratory values will be provided when the laboratory parameter has both high and low grading criteria. The denominator for the percentage calculation will be the number of participants in the baseline category. The number of participants who experienced worsening of laboratory abnormalities will be summarized by maximum postbaseline severity.

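### The mmol/L form of the FLIPI hemoglobin cut-off in Protocol Appendix E does not equal 120 g/L; if current FLIPI was scored from mmol/L values, some subjects would lose a point.

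*Protocol*

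**What the plan says.** Protocol Appendix E is the FLIPI scoring table. Its hemoglobin row awards one point below 120 g/L and restates that cut-off in two other units, "12.0 g/dL or 6.37 mmol/L". Protocol Section 1.1, which points to Appendix E, describes the same factor as "hemoglobin less than 120 g/L" and gives no mmol/L value. The lower part of the table, "Risk Group by FLIPI Total Point Score", assigns low risk to a total of 0 or 1, intermediate to 2, and high to 3 or more.

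The SAP uses the resulting category twice. Section 6.1.2 includes "current FLIPI risk category" in the baseline disease history for the full analysis set. Section 7.3.2 lists "Current FLIPI risk category" among the ORR subgroups, with the same three bands as Appendix E, and the subgroup results go into a forest plot.

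On units, SAP Section 9.3.2 says "All test results and associated normal ranges from central laboratories will be reported in SI units" but does not name the hemoglobin unit. The eligibility floor in Protocol Section 3.1 is in g/dL: "Hemoglobin ≥ 8.0 g/dL". Neither document says who derives FLIPI or from which unit.

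**The concern.** Three expressions of one cut-off should classify every subject identically. Here the g/L and g/dL forms agree with each other and with Section 1.1, but the mmol/L form is a lower threshold. The table therefore holds two different rules for one criterion, and the choice between them depends only on the unit in front of the person scoring.

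The discrepancy runs in one direction. Scoring in mmol/L can only remove a point, so any misclassified subject would look lower risk than the g/L rule makes them. At stake is the content of the current FLIPI baseline summary and of the FLIPI rows in the ORR subgroup display.

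**Working it through.** **Inputs.** From Appendix E: 120 g/L, 12.0 g/dL, 6.37 mmol/L and the three risk bands. From Protocol 3.1: the hemoglobin floor of 8.0 g/dL. The molar mass of hemoglobin is not in the documents. It is taken as an assumption: 16.0 to 16.2 g/mmol per monomer (central value 16.114), with about 64.5 g/mmol for the tetramer as an alternative.

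**Step 1: the g/dL form.** 120 / 10 = 12.0 g/dL. The printed figure is reproduced.

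**Step 2: the mmol/L form.** The formula is mmol/L = (g/L) / (g/mmol).

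| Assumed molar mass (g/mmol) | 120 g/L in mmol/L | 6.37 mmol/L in g/dL |
|---|---|---|
| 16.0 | 120 / 16.0 = 7.50 | 6.37 × 16.0 / 10 = 10.19 |
| 16.114 | 120 / 16.114 = 7.447 | 6.37 × 16.114 / 10 = 10.26 |
| 16.2 | 120 / 16.2 = 7.41 | 6.37 × 16.2 / 10 = 10.32 |
| 17.0 (deliberately generous) | 120 / 17.0 = 7.06 | 6.37 × 17.0 / 10 = 10.83 |
| 64.5 (tetramer) | 120 / 64.5 = 1.86 | 6.37 × 64.5 / 10 = 41.09 |

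No row gives 6.37. The molar mass that would give it is 120 / 6.37 = 18.84 g/mmol, which fits neither basis. Relative to 7.447, the printed figure is 1 − 6.37 / 7.447 = 14.5% too low. In g/dL the gap is 12.0 − 10.26 = 1.74.

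**Step 3: who would be scored differently.** The criterion is below the cut-off. A hemoglobin from 6.37 to below about 7.45 mmol/L, that is from about 10.3 to below 12.0 g/dL, scores 1 under the g/L or g/dL rule and 0 under the printed mmol/L rule. The whole interval lies above the 8.0 g/dL floor, so such subjects can be enrolled.

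**Step 4: what losing the point does to the risk group.**

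| True score | Score after losing the point | Group before | Group after | Changed? |
|---|---|---|---|---|
| 1 | 0 | low | low | no |
| 2 | 1 | intermediate | low | yes |
| 3 | 2 | high | intermediate | yes |
| 4 | 3 | high | high | no |
| 5 | 4 | high | high | no |

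A wrong group therefore needs three things together: scoring in mmol/L, a hemoglobin inside the interval, and a true total of 2 or 3.

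**The case against.** The strongest reply concerns reach, not arithmetic. Nothing in the documents shows hemoglobin being scored in mmol/L. Elsewhere the protocol uses g/L and g/dL, Appendix E leads with g/L, and mmol/L appears only in its parenthesis. The SI-units sentence in SAP 9.3.2 governs laboratory summaries, names no hemoglobin unit and says nothing about FLIPI. Protocol 6.1 bases eligibility on central hematology. Protocol 7.5.6 sends laboratory work to a central laboratory unless otherwise specified and admits local values to the eCRF only in limited circumstances. Baseline hemoglobin should therefore come mainly from one source and not vary by site. FLIPI is also one of twelve descriptive ORR subgroup factors, and SAP 7.1 states no efficacy hypotheses.

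All of that stands, and it limits the consequence. It does not rescue the number: Appendix E is current text, no other section corrects it, and the central-laboratory rules do not say which unit the scorer reads.

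Two stronger readings are tempting. A reader might infer that an appreciable share of the trial sits in the wrong risk group. The documents give no baseline hemoglobin distribution, no prevalence of the other four factors and no count of subjects scored in mmol/L, so no such share can be derived. A reader might also infer that the initial FLIPI category in SAP 6.1.2 is affected. It is listed with initial grade and staging as disease history, and nothing says it was scored with Appendix E.

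**Conclusion.** Wrong as written. The mmol/L figure in Appendix E is about 14.5% below the value that matches 120 g/L. That value is about 7.45 mmol/L, or 7.41 to 7.50 over the assumed monomer molar mass of 16.0 to 16.2 g/mmol. The conclusion rests on a molar mass from outside the documents, but neither the monomer nor the tetramer basis yields 6.37.

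The effect on results is conditional and may be nil. If current FLIPI hemoglobin was scored in g/L or g/dL, nothing changes. If it was scored in mmol/L, the number misplaced cannot be estimated from the documents. The exposure is confined to the current FLIPI summary and its ORR subgroup rows. Eligibility does not use FLIPI, and the overall ORR and the futility count do not depend on it. This is a small correction, but more than cosmetic, because the table defines a category that the SAP analyzes.

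**What to change.** In Protocol Appendix E, replace 6.37 mmol/L with 7.45 mmol/L, or delete the mmol/L figure and leave g/L and g/dL. Confirm and record the unit in which current FLIPI hemoglobin was scored. If any subject was scored in mmol/L, re-check those with values between 6.37 and 7.45 mmol/L against 120 g/L and correct the category where the total crosses a band. No new SAP derivation is needed for this.

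The cost is one number, one confirmation and, at most, a short data check within a study of about 120 subjects. Enrolment, the primary analysis and the interim rule stay as they are.

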APPENDIX F. PROTOCOL AMENDMENT SUMMARY OF CHANGES

Document	Date
Amendment (Version) 1:	15 MAR 2017
Amendment (Version) 2:	15 AUG 2017
Amendment (Version) 3:	11 SEP 2017
Amendment (Version) 4:	25 OCT 2017
Amendment (Version) 4-CAN:	12 DEC 2017
Amendment (Version) 5:	17 JAN 2018
Amendment (Version) 6:	11 JUL 2018
Amendment (Version) 7:	04 SEP 2018
Amendment (Version) 8:	06 DEC 2018
Amendment (Version) 9:	23 DEC 2019

Amendment 9 (23 DEC 2019)

Overall Rationale for the Amendment: The primary purpose of this amendment is to provide additional guidance on dose modification in the event of diarrhea and colitis and to define the end of the study, including the option to receive continued treatment with INCB050465 in a rollover protocol.

1. **Section 5.4.1.1, Dose Modifications (Table 3: Guidelines for Interruption and Restarting INCB050465; Table 4: Dose Levels and Reductions for INCB050465); Section 5.4.1.2, Supportive Care Guidelines for Diarrhea/Colitis (Table 5: Guidelines for Dose Modification of INCB0050465 for Diarrhea/Colitis)**

Description of change: Revision to text pertaining to interruptions and restarting INCB050465 for adverse events of diarrhea and colitis.

Rationale for change: To provide additional dose modifications of INCB050465 for diarrhea and colitis.

2. **Synopsis; Section 4.5, Overall Study Duration; Section 5.8, Treatment After the End of the Study; Section 6.5, End of Study**

Description of change: Text and new section added to describe that subjects who are receiving active study treatment and have no evidence of progressive disease at the end of the study will have the option to continue on INCB050465 provided within a rollover Protocol.

Rational for change: To clarify what treatment options are available at the end of the study.

3. **Synopsis (Estimated Number of Subjects, Statistical Methods); Section 4.1, Overall Study Design; Section 4.3.1, Planned Number of Subjects; Section 4.5, Overall Duration; Section 9.2, Selection of Sample Size; Section 9.4.1.1, Primary Efficacy Analyses**

Description of change: Increased the target enrollment from approximately 100 to approximately 120 subjects and changed the timing of the primary analysis.

Rational for change: To align with recommendations from the US FDA.

4. **Synopsis (Estimated Duration of Participation); Section 4.4, Duration of Treatment and Subject Participation; Section 4.5, Overall Study Duration; Section 5.7, Criteria for Study Discontinuation; Section 6.5, End of Study**

Description of change: Text and new section added to define the following: a) criteria for a subject to be discontinued from the study and b) the end of study.

Rational for change: To clarify when a subject will be discontinued from the study and when the study will end.

5. **Synopsis (Study Schedule/Procedures); Section 6, Study Assessments (Table 6: Schedule of Assessments)**

Description of change: Changed frequency of study treatment dispensation and assessment of compliance from every 4 weeks to every 12 weeks starting at Week 48.

Rationale for change: To reduce the burden of extra pharmacy visits for the subjects.

6. **Section 9.1, Study Populations**

Description of change: Removed the PP population.

Rationale for change: For a single-arm, open-label study, the determination of subjects to be excluded from the PP population is post hoc and may not be done objectively; thus, analysis based on this population may not be meaningful.

7. **Section 9.4.2.4, Electrocardiograms (Table 11: Criteria for Clinically Notable Electrocardiogram Abnormalities)**

Description of change: Changed high threshold of QTcF interval from > 460 msec to > 450 msec for analysis purposes.

Rationale for change: To comply with the categories outlined in FDA Guidance for Industry (E14 Clinical Evaluation of QT/QTc Interval Prolongation and Proarrhythmic Potential for Non-Antiarrhythmic Drugs) used to characterize outliers in QTc values.

8. **Incorporation of administrative changes.** Other minor, administrative changes have been incorporated throughout the Protocol and are noted in the redline version of the amendment.

This amendment also incorporates the following from Protocol Administrative Change 3 dated 23 MAY 2019:

[REDACTED]

Amendment 8 (06 DEC 2018)

Overall Rationale for the Amendment: The primary purpose of the amendment is to stop the 1:1 allocation of subjects after the 50th subject has enrolled and to enroll the remaining 50 subjects to only one of the 2 treatment regimens being evaluated.

1. **Synopsis; Section 4.1, Overall Study Design (Figure 2: Study Design); Section 9.2, Selection of Sample Size**

Description of change: Revised to state that after 50 subjects are enrolled, the remaining 50 subjects will be enrolled to only one of the 2 treatment regimens being evaluated in this study. Patients allocated to the unselected treatment will be allowed to cross over.

Rationale for change: To increase the number of subjects administered one of the 2 treatment regimens, leading to a better understanding of the long-term safety and efficacy of that treatment regimen.

2. **Section 10.4, Data Privacy and Confidentiality of Study Records**

Description of change: Revised language pertaining to the protection of personal data.

Rationale for change: To comply with the General Data Protection Regulation 2016/679.

3. **Incorporation of administrative changes.** Other minor, administrative changes have been incorporated throughout the Protocol and are noted in the redline version of the amendment.

Amendment 7 (04 SEP 2018)

Overall Rationale for the Amendment: The primary purpose of this amendment is to provide a list of CYP3A inhibitors and inducers.

1. **Section 3.2, Subject Exclusion Criteria; Section 5.6.2, Restricted Medications; Section 5.6.3, Prohibited Medications and Therapies; Appendix B, CYP3A Inhibitors and Inducers**

Description of change: Added tables of CYP3A inhibitors and inducers in Appendix B. These tables were updated and modified compared to the previous versions, which had been removed from Protocol Version 6 and placed in the Pharmacy Manual.

Rationale for change: These tables were returned to the Protocol by the request of the European Health Authority.

Amendment 6 (11 JUL 2018)

Overall Rationale for the Amendment: The primary purpose of this amendment is to modify the dose reduction schedules.

1. Section 5.4.1.1, Dose Modifications (Table 4, Dose Levels for INCB050465)

Description of change: Modified the dose reduction schedules.

Rationale for change: The new schedules are being implemented to ensure that all subjects will remain on a QD dosing schedule for the first 8 weeks (56 days) and to provide consistency between Treatments A and B.

2. Section 5.4.1.1, Dose Modifications (Table 3, Guidelines for Interruption and Restarting INCB050465)

Description of change: Redefined “Grade 3 or Grade 4 ANC with an oral temperature of at least 38.5°C OR with Grade ≥ 3 infection” as Grade 3 or Grade 4 febrile neutropenia. Allowance is made to restart INCB050465 at the same dose after Grade 4 ANC, Grade 4 platelet count, or Grade 3 or Grade 4 febrile neutropenia resolve to \leq Grade 2, rather than Grade 1, regardless of attribution.

Rationale for change: A restart at the same dose level regardless of attribution is allowed to provide study doctors flexibility in subject management. Dosing is allowed to begin at \leq Grade 2 to be consistent with eligibility criteria, which start at Grade 2 for neutrophil and platelet counts.

3. Section 7.5.6, Laboratory Assessments

Description of change: Clarified the scenarios in which a local laboratory assessment may be performed and in which cases local laboratory values would be entered into the eCRF.

Rationale for change: Clarification.

4. Section 7.6.2, Bone Marrow Examination

Description of change: Clarified that bone marrow collected at screening and postbaseline should be sent to a local histopathology laboratory. [REDACTED]

Rationale for change: Clarification.

5. Section 3.1, Subject Inclusion Criteria (Inclusion Criterion 9d)

Description of change: Inclusion Criterion 9d was revised to allow subjects with whose total bilirubin values are $> 1.5 \times$ ULN to enroll if the elevation is due to Gilbert’s syndrome.

Rationale for change: Gilbert’s syndrome is a hereditary condition characterized by intermittent, unconjugated hyperbilirubinemia in the absence of hepatocellular damage and hemolysis. Consistent with other PI3K δ inhibitors, elevated bilirubin due to Gilbert’s syndrome is not expected to alter the risk/benefit profile for subjects taking INCB050465.

6. **Section 7.4, Prior and Concomitant Medications and Procedures**

Description of change: Added a definition for lines of therapy.

Rationale for change: Definitions were added to improve consistency for calculation of prior lines of therapy.

7. **Section 3.2, Subject Exclusion Criteria; Section 5.6.2, Restricted Medications; Section 5.6.3, Prohibited Medications and Therapies; Appendix B, Cytochrome P450 Inhibitors and Cytochrome P450 Inducers**

Description of change: Deleted Appendix B and references to Appendix B.

Rationale for change: Information was moved to the Pharmacy Manual.

8. **Incorporation of administrative changes.** Other minor, administrative changes have been incorporated throughout the Protocol and are noted in the redline version of the amendment.

Amendment 5 (17 JAN 2018)

This amendment is considered to be nonsubstantial based on the criteria set forth in Article 10(a) of Directive 2001/20/EC of the European Parliament and the Council of the European Union because it neither significantly impacts the safety or physical/mental integrity of participants nor the scientific value of the study.

Overall Rationale for the Amendment:

The primary purpose of this amendment is to institute hematology testing every 2 weeks for the first 8 weeks of dosing.

1. **Synopsis; Section 6, Study Assessments (Table 6, Schedule of Laboratory Assessments)**

Description of change: Study visits were added at Week 2 and Week 6 for hematology testing.

Rationale for change: Requested by the US FDA.

2. **Section 5.5.1, Criteria for Study Treatment Discontinuation**

Description of change: The following bullet has been deleted from Section 5.5.1:

If a subject is found not to have met eligibility criteria, then the medical monitor and investigator will collaborate to determine whether the subject should be withdrawn from the study.

Rationale for change: Requested by Health Canada.

3. **Section 5.4.1.2, Supportive Care Guidelines for Neutropenia and Thrombocytopenia**

Description of change: Provided instructions to investigators to remind subjects to report signs or symptoms of infection, bleeding, or sudden, extremely painful headaches.

Rationale for change: Requested by the US FDA.

4. **Section 5.6.2, Restricted Medications; Section 5.6.3, Prohibited Medications and Therapies**

Description of change: Radiation therapy was removed from Section 5.6.3 as it was redundant with Section 3.2 (exclusion criterion 10), which lists excluded, concurrent anticancer therapies. A description of permitted radiotherapy was added to Section 5.6.2. The length of time a live vaccine is prohibited was added to Section 5.6.3.

Rationale for change: Administration of localized radiotherapy in cases of pain or impending compression fractures may be permitted to allow subjects who are otherwise benefitting to continue study treatment. The length of time a live vaccine is prohibited was added to align with other clinical studies within the INCB050465 development program..

7. Appendix A, Information Regarding Effectiveness of Contraceptive Methods

Description of change: Provided information for male contraception methods.

Rationale for change: Informational.

- 8. Incorporation of administrative changes.** Other minor, administrative changes have been incorporated throughout the Protocol and are noted in the redline version of the amendment.

Amendment 4-CAN (12 DEC 2017)

Overall Rationale for the Amendment:

To remove a criterion for study treatment discontinuation per Health Canada's request.

1. Section 5.5.1, Criteria for Study Treatment Discontinuation

Description of change: The following bullet has been deleted from Section 5.5.1:

- If a subject is found not to have met eligibility criteria, then the medical monitor and investigator will collaborate to determine whether the subject should be withdrawn from the study.

Rationale for change: To meet Health Canada requirements.

Amendment 4 (25 OCT 2017)

Overall Rationale for the Amendment:

The primary purpose of this amendment is to remove the comparator arm (idelalisib) from the study.

This amendment includes the changes to Protocol INCB 50465-203 Amendment 3 (11 SEP 2017) summarized below. A redline version of the amendment depicting the updated and previous text is also provided.

- 1. Title; Synopsis; Section 1, Introduction; Section 2, Study Objectives and Endpoints; Section 3.2, Subject Exclusion Criteria; Section 4.1, Overall Study Design; Section 4.2, Measures Taken to Avoid Bias; Section 4.3.1, Planned Number of Subjects; Section 4.5, Overall Study Duration; Section 5.1.2, Randomization and Blinding; Section 5.2, Study Treatments; Section 5.4, Treatment Interruptions and Adjustments; Section 5.6, Concomitant Medications; Section 6, Study Assessments (Table 6, Schedule of Assessments; Table 7, Schedule of Laboratory Assessments); Section 6.1, Screening; Section 6.2, Treatment; Section 7.2, Interactive Response Technology Procedure; 7.4, Prior and Concomitant Medications and Procedures; 7.5.6.1, Chemistry and Hematology; Section 7.6, Efficacy Assessments; Section 7.7.1, Blood Sample Collection; Section 9, Statistics; Appendix A, Information Regarding Effectiveness of Contraceptive Methods.**

Description of change: The comparator arm, idelalisib, was removed from the study, allowing for removal of the biweekly assessments for ANC and liver enzymes required for idelalisib and reduction in the number of subjects from 180 to 100.

Rationale for change: A PI3K inhibitor, copanlisib, was recently granted accelerated approval by the US Food and Drug Administration in the patient population being evaluated in this study. Therefore, the PI3K δ inhibitor, idelalisib, can no longer be considered the standard of care in the US and consequently is not a relevant comparator for new PI3K inhibitors. It is also not feasible to replace idelalisib with copanlisib, which is currently approved only in the US. This change allows the number of subjects to be reduced from 180 to 100.

- 2. Section 3.1, Inclusion Criteria**

Description of change: Removed South Korea–specific age requirement.

Rationale for change: Study will not be conducted in South Korea

- 3. Section 3.2, Subject Exclusion Criteria**

[figure not shown]
Description of change: Exclusion criterion 17 (liver disease) was updated.

Rationale for change: As there have been no reported HBV or HCV reactivations in INCB 50465-101, the exclusion criterion was amended to align with those of approved PI3K inhibitors.

4. **Section 5.2.1.2, Supply, Packaging, and Labeling; Section 5.6.1, *Pneumocystis Jirovecii* Prophylaxis**

Description of change: Moved text describing procurement of drugs required for PJP prophylaxis.

Rationale for change: Administrative.

6. **Appendix E, Lugano Classification for Response Assessment**

Description of change: Removed the column describing PET-based criteria of response.

Rationale for change: The study is based on CT/MRI only.

[figure not shown]
7. **Incorporation of administrative changes.** Other minor, administrative changes have been incorporated throughout the Protocol and are noted in the redline version of the amendment, including the addition of all summary of changes to Appendix G.

Amendment 3 (11 SEP 2017)

Overall Rationale for the Amendment:

The primary purpose of this amendment is to address changes requested by the European Regulatory Agency.

[figure not shown]
This amendment includes the changes to Protocol INCB 50465-203 Amendment 2 (15 AUG 2017) summarized below. A redline version of the amendment depicting the updated and previous text is also provided.

2. Section 9.4.1.1, Primary Efficacy Analyses

Description of change: Added a description of the subgroup analysis, which will include subgroups based on age, gender, and geographic region that can be further divided or combined based on emerging data.

Rationale for change: Requested by the European Regulatory Agency.

Amendment 2 (15 AUG 2017)

Overall Rationale for the Amendment:

The primary purpose of this amendment is to address changes requested by the European Regulatory Agency.

This amendment includes the changes to Protocol INCB 50465-203 Amendment 1 (15 MAR 2017) summarized below. A redline version of the amendment depicting the updated and previous text is also provided.

1. Title page

Description of change: The EudraCT number has been added (2017-001624-22).

Rationale for change: Informational.

2. Synopsis; Section 6, Study Assessments (Table 7)

Description of change: The frequency of cytomegalovirus analysis was increased to every 4 weeks.

Rationale for change: Requested by European Regulatory Agency.

3. Section 3.2, Subject Exclusion Criteria (criterion 16); Section 6, Study Assessments (Tables 7 and 8); Section 7.5.6.4, HIV Screening Test

Description of change: Revised to require that subjects enrolled outside the United States have an HIV test at screening.

Rationale for change: Requested by European Regulatory Agency.

4. Section 5.4.2, Criteria and Procedures for Dose Interruptions or Adjustments of Idelalisib

Description of change: Clarified that investigators should follow the individual product package insert for safety assessments for idelalisib.

Rationale for change: Requested by European Regulatory Agency.

5. Section 6, Study Assessments (Table 7)

Description of change: Stated that blood counts should be monitored at least weekly in subjects receiving either idelalisib or INCB050465 while ANC is $< 1.0 \times 10^9/L$, and referenced the product package insert and Section 5.4, respectively.

Rationale for change: Requested by European Regulatory Agency.

6. Section 6, Study Assessments (Table 7)

Description of change: Added a serum pregnancy test at the safety follow-up visit for women of child-bearing potential.

Rationale for change: Requested by European Regulatory Agency.

7. **Appendix A, Information Regarding Effectiveness of Contraceptive Methods**

Description of change: Revised to require that women receiving idelalisib who are using hormonal contraceptives add a barrier method as a second form of contraception, and removed the statement that the investigational medicinal products (IMP), which included INCB050465, may reduce the efficacy of hormonal contraceptives.

Rationale for change: The addition of a barrier method was requested by European Regulatory Agency per the SmPC. The statement that the IMP may reduce the efficacy of hormonal contraceptives was removed as the IMP includes INCB050465, which unlike idelalisib, is not a CYP3A4 inhibitor and therefore has no effect on hormonal contraception.

8. **Synopsis; Section 2, Study Objectives and Endpoints (Table 1)**

Description of change: The primary objective was revised to state the threshold for conducting a superiority analysis.

Rationale for change: Requested by European Regulatory Agency.

9. **Synopsis; Section 9, Statistics**

Description of change: Clarified that descriptive summaries for categorical variables will include the number and percentage of subjects in each category, and that the descriptive summaries for continuous variables will include the number of observations, mean, standard deviation, median, minimum, and maximum.

Rationale for change: Requested by European Regulatory Agency.

10. **Synopsis; Section 9.4.1.1, Primary Efficacy Analyses**

Description of change: Clarified that the point estimates and confidence intervals (CIs) will be calculated for the primary endpoint of objective response rate for INCB050465 and idelalisib and their difference, and clarified the timing for the primary endpoint.

Rationale for change: Requested by European Regulatory Agency.

11. **Section 9.4.1.1, Primary Efficacy Analyses**

Description of change: Clarified that subjects without sufficient baseline or on-study response assessment information to be adequately assessed for response status will be considered as nonresponders and included in the denominators in the calculations of ORR.

Rationale for change: Requested by European Regulatory Agency.

12. **Section 9.4.1.3, Other Efficacy Analyses**

Description of change: Clarified that ORR, complete response rate (CRR), duration of response (DOR), progression-free survival (PFS), and overall survival (OS) will be summarized by treatment groups. Point estimates and 95% CIs will be provided for ORR and CRR. Kaplan-Meier estimations of median DOR, PFS, and OS and their 95% CIs will also be calculated for each group.

Rationale for change: Requested by European Regulatory Agency.

13. **Incorporation of administrative changes.** Other minor, administrative changes have been incorporated throughout the Protocol and are noted in the redline version of the amendment.

Amendment 1 (15 MAR 2017)

